6.12 Lost To Follow Up

In the event that a patient has been lost to follow up, this should be recorded on the eCRF with their last known contact date and survival status at the time. Lost to follow up status and steps taken to try to contact patient should also be noted in the patient's medical notes.

6.13 Trial Closure

End of trial is defined as collection of the last data point of the last patient, which is 1 year after their second evacuation visit. Samples taken for ongoing research will be registered with the Imperial College Tissue Bank at this point to support ongoing work. In the event that the study is closed early or terminated, the sponsor will notify the participating site that all study related activities will need to stop. Patients are to continue being cared for as per Trusts standard procedures.

7. PHARMACOVIGILANCE

7.1 Definitions

Adverse Event (AE): any untoward medical occurrence in a patient or clinical trial subject administered a medicinal product and which does not necessarily have a causal relationship with this treatment. *An AE can therefore be any unfavourable and unintended sign (including an abnormal laboratory finding), symptom, or disease temporally associated with the use of an investigational medicinal product (IMP), whether or not considered related to the IMP.*

Adverse Reaction (AR): all untoward and unintended responses to an IMP related to any dose administered. *All AEs judged by either the reporting investigator or the sponsor as having reasonable causal relationship to a medicinal product qualify as adverse reactions. The expression reasonable causal relationship means to convey in general that there is evidence or argument to suggest a causal relationship.*

Unexpected Adverse Reaction: an AR, the nature or severity of which is not listed in the reference safety information (RSI) e.g. list of expected medical events within investigator's brochure for an unapproved investigational product or section 4.8 of the summary of product characteristics (SmPC) for an authorised product. *When the outcome occurs this adverse reaction should be considered as unexpected. Side effects documented in the SmPC which occur in a more severe form than anticipated are also considered to be unexpected.*

Serious Adverse Event (SAE) or Serious Adverse Reaction: any untoward medical occurrence or effect that at any dose:

- **Results in death.**
- **Is life-threatening** – refers to an event in which the subject was at risk of death at the time of the event; it does not refer to an event which hypothetically might have caused death if it were more severe.
- **Requires hospitalisation, or prolongation of existing inpatients' hospitalisation.**
- **Results in persistent or significant disability or incapacity.**
- **Is a congenital anomaly or birth defect.**

Medical judgement should be exercised in deciding whether an AE/AR is serious in other situations. Important AE/ARs that are not immediately life-threatening or do not result in death or hospitalisation but may jeopardise the subject or may require intervention to prevent one of the other outcomes listed in the definition above, should also be considered serious.

Suspected Unexpected Serious Adverse Reaction (SUSAR): any suspected adverse reaction related to an IMP that is both unexpected and serious

7.2 Causality

Most adverse events and adverse drug reactions that occur in this study, whether they are serious or not, will be expected treatment-related toxicities due to the drugs used in this study. The assignment of the causality should be made by the investigator responsible for the care of the participant using the definitions in the table below.

If any doubt about the causality exists the local investigator should inform the study coordination centre who will notify the Chief Investigators. The pharmaceutical companies and/or other clinicians may be asked to advise in some cases.

In the case of discrepant views on causality between the investigator and others, all parties will discuss the case. In the event that no agreement is made, the MHRA will be informed of both points of view.

Relationship	Description
Unrelated	There is no evidence of any causal relationship
Unlikely	There is little evidence to suggest there is a causal relationship (e.g. the event did not occur within a reasonable time after administration of the trial medication). There is another reasonable explanation for the event (e.g. the participant's clinical condition, other concomitant treatment).
Possible	There is some evidence to suggest a causal relationship (e.g. because the event occurs within a reasonable time after administration of the trial medication). However, the influence of other factors may have contributed to the event (e.g. the participant's clinical condition, other concomitant treatments).
Probable	There is evidence to suggest a causal relationship and the influence of other factors is unlikely.
Definitely	There is clear evidence to suggest a causal relationship and other possible contributing factors can be ruled out.
Not assessable	There is insufficient or incomplete evidence to make a clinical judgement of the causal relationship.

RESOLVE	C/43/2022	Imperial College London	v2.0 10 th July 2023
---------	-----------	-------------------------	------------------------------------

7.3 Severity of Adverse Events

Severity of AEs will be assessed using the grading scales found in the National Cancer Institute CTCAE version 5.0 (27th November 2017), by attributing the most relevant CTCAE term. Where it is not possible to attribute a specific CTCAE term, a term may be attributed by the investigator and assessed according to the introduction under Grades in CTAE version 5.0 i.e., grade 1=mild; grade 2=moderate; grade 3=severe; grade 4=life-threatening; grade 5= fatal.

CTCAE version 5.0 is accessible online here:

https://ctep.cancer.gov/protocoldevelopment/electronic_applications/ctc.htm

7.4 Reporting Procedures

All adverse events should be reported. Depending on the nature of the event the reporting procedures below should be followed. Any questions concerning adverse event reporting should be directed to the study coordination centre in the first instance. A flowchart is given below to aid in the reporting procedures.

(i) 7.4.1 Non serious AR/AEs

All such toxicities, whether expected or not, should be recorded in the toxicity section of the relevant case report form and sent to the study coordination centre within one month of the form being due.

(ii) 7.3.2 Serious AR/AEs

Fatal or life threatening SAEs and SUSARs should be reported on the day that the local site is aware of the event. The SAE form asks for nature of event, date of onset, severity, corrective therapies given, outcome and causality (i.e. unrelated, unlikely, possible, probably, definitely). The responsible investigator should sign the causality of the event. Additional information should be sent within 5 days if the reaction has not resolved at the time of reporting.

SAEs

An SAE form should be completed and emailed to the study coordination centre for all SAEs within 24 hours. However, relapse and death due to disease under study and hospitalisations for elective treatment of a pre-existing condition do not need reporting as SAEs.

SUSARs

In the case of suspected unexpected serious adverse reactions, the staff at the site should:

Complete the SAE case report form & send it immediately (within 24 hours,), signed and dated to the study coordination centre together with relevant treatment forms and anonymised copies of all relevant investigations.

[figure not shown]
Or

Contact the study coordination centre by phone and then send the completed SAE form to the study coordination centre within the following 24 hours as above.

The study coordination centre will notify the MHRA, REC and the Sponsor of all SUSARs occurring during the study according to the following timelines; fatal and life-threatening within 7 days of notification and non-life threatening within 15 days. All investigators will be informed of all SUSARs occurring throughout the study.

Local investigators should report any SUSARs and /or SAEs as required by their Local Research Ethics Committee and/or Research & Development Office

Safety Reporting Overview

* Unless identified in the protocol as not requiring immediate reporting

Contact Details for Reporting SAEs and SUSARs:

[contact]

7.5 Developmental Safety Update Reports / Annual Safety Reports

Developmental Safety Update Reports (DSUR) will be submitted to the Sponsor, the Ethics Committee and Regulatory Authority in accordance with local / national regulatory requirements.

7.6 Pregnancy

Pembrolizumab is contraindicated in pregnancy. Pregnancy is not considered an SAE but where the patient gives their consent the pregnancy will be recorded and followed up in the eCRF.

7.7 Reporting urgent safety measures

If any urgent safety measures are taken the CI/Sponsor shall immediately and in any event no later than 3 days from the date the measures are taken, give written notice to the MHRA and the relevant REC of the measures taken and the circumstances giving rise to those measures.

8. STATISTICAL ANALYSES

8.1 Sample Size and power considerations

8.1.1 Feasibility of the treatment strategy

A primary goal of the study is to determine the proportion of patients in the treatment arm who complete the planned protocol of pembrolizumab followed by second evacuation. To justify a larger study of this intervention, we would expect 90% of patients to complete the protocol with a lower bound of 70% below which we would not consider the strategy to be practicable. With 10 patients, assuming 90% complete protocol treatments, the 95% confidence interval is 71 – 100%.

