3.2 Treatment regimens

Table 1: Summary of treatment groups

Treatment arm	Number of participants
Second evacuation alone (control)	10
Pembrolizumab followed by second evacuation (Intervention)	10
Total number of participants	20

Figure 1: Study Flowchart

Key:

CHM – Complete Hydatidiform mole; **1ry** – Primary; **CPI** – Checkpoint inhibitor; **Pembro** – Pembrolizumab; **FU** – Follow up Visit

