8.1.2 Feasibility of recruitment

Estimated cure rate with second evacuation alone is approximately 25% in our cohort³. The cure rate with single agent chemotherapy is approximately 66%. Therefore under conservative assumptions, in order to demonstrate a clinically significant benefit of pembrolizumab prior to second evacuation of 66% cure vs. second evacuation alone (25% cure), 40 patients in total are required (80% power, significance level 0.05). To justify a larger study, this cohort would be recruited in no more than 3 years (14 patients/year).

Based on current caseloads, we estimate approximately 50 patients per year in the UK are eligible for the study, of whom 30 are managed at CXH. With 30 eligible patients, assuming 66% (n=20) are recruited in 1 year, the 95% confidence interval

is 50 – 84%. This is consistent with the recruitment target of at least 15 patients per year at CXH (30 patients/year x 0.5 [lower bound of the 95% confidence interval for the recruitment rate]). Thus recruitment of 20 patients in 1 year would give us confidence that a definitive study would be feasible.

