8.3.2 Primary Endpoint Analysis

We will carry out descriptive data analyses with respect to the feasibility of recruitment and completing protocolled treatments on the intervention arm.

Firstly, participant flows will be evaluated using a CONSORT diagram adapted for feasibility studies³⁸. We will record the numbers of patients:

1. With low risk GTN following primary evacuation of CHM
2. Consented
3. Screened
4. Eligible
5. Randomised
6. Who complete per protocol treatments

The number of patients who drop-out at each stage will additionally be recorded.

We will calculate the proportion of eligible patients who consent to participation as a measure of the potential to recruit to a larger study, along with the proportion of patients randomised to the intervention arm who complete per protocol treatments. In the intervention arm, the proportion of patients who are withdrawn from the study after pembrolizumab but before second evacuation and the reasons for this. The 95% confidence intervals will be calculated along with these proportions.

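### Section 8.1.1: the 71–100% interval for 9 of 10 completers is a truncated Wald interval; valid methods put the lower limit at about 55–63%, below the 70% floor

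*Protocol*

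**What the plan says.** Section 2.1 makes the proportion of intervention-arm patients who complete protocol treatment one of two primary feasibility endpoints. Section 3.2 allots 10 patients to that arm.

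For this endpoint, section 8.1.1 gives an expectation and a floor: "we would expect 90% of patients to complete the protocol with a lower bound of 70% below which we would not consider the strategy" practicable. The next sentence gives the precision: "With 10 patients, assuming 90% complete protocol treatments, the 95% confidence interval is 71 – 100" (per cent). No interval method is named.

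Section 8.1.2 handles recruitment in a similar way. There the yearly target is derived explicitly from the "lower bound of the 95% confidence interval for the recruitment rate". Section 8.1.4 closes by concluding that 10 patients per arm is justified. For the analysis, section 8.3.2 says: "The 95% confidence intervals will be calculated along with these proportions", again without naming a method.

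**The concern.** With 10 patients and an expected proportion of 90%, only one non-completer is expected. The normal approximation to the binomial is poor there, and an upper limit of exactly 100% alongside an observed failure suggests truncation. The printed lower limit of 71% falls just above the 70% floor in the preceding sentence. If that 1-point margin comes only from the formula, then the apparent match between 10 patients and the 70% floor is not real. The expected result of 9 of 10 would then not exclude a completion rate that the protocol itself calls impracticable.

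**Working it through.** **Inputs.** n = 10 (sections 3.2 and 8.1.1); assumed proportion p = 0.90, i.e. 9 of 10 (8.1.1); 95%, taken as two-sided because two limits are given (8.1.1); floor 70% (8.1.1).

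**1. Reproducing the printed interval.** Wald: p ± 1.96·√(p(1−p)/n).
- Standard error = √(0.9 × 0.1 / 10) = 0.0949
- 0.90 ± 1.96 × 0.0949 = 0.714 to 1.086
- Cut at 1.00: 71–100%, as printed.

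No other method tried gives a lower limit of 71%.

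**2. Clopper-Pearson, 9/10.** The lower limit solves P(X ≥ 9 | p) = 0.025, that is p⁹(10 − 9p) = 0.025. At p = 0.555, p⁹ ≈ 0.0050 and 10 − 9p ≈ 5.005, with product 0.025. Interval: **55.5–99.7%**.

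**3. Wilson, 9/10.** [p + z²/2n ± z·√(p(1−p)/n + z²/4n²)] / (1 + z²/n), with z² = 3.8416.
- Centre term: 0.9 + 0.1921 = 1.0921
- Half-width term: 1.96 × √(0.0090 + 0.0096) = 0.2673
- Divisor: 1.3842
- Interval: **59.6–98.2%**.

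**4. Lower limits by other methods, 9/10.**

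| Method | Lower limit |
|---|---|
| Logit | 53.3% |
| Wilson, continuity-corrected | 54.1% |
| Blaker | 55.6% |
| Agresti-Coull | 57.4% |
| Mid-P | 59.7% |
| Jeffreys, equal-tailed | 61.9% |
| Likelihood ratio | 62.8% |
| Arcsine | 65.1% |
| Jeffreys, highest density | 66.9% |
| Wald with t quantile | 67–69% |
| *Wald as printed* | *71.4%* |

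All but the printed one are below 70%.

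**5. Does 9 of 10 exclude 70%?** P(X ≥ 9 | n = 10, p = 0.70) = 0.7⁹ × (10 − 6.3) = 0.0404 × 3.7 = 0.149. It does not.

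**6. The best possible result, 10/10.** Clopper-Pearson lower limit = 0.025^(1/10) = 69.2%; Wilson lower limit = 10/13.84 = 72.2%. Wald collapses to 100–100%.

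**7. Wald coverage at n = 10.**
- True rate 90%: the interval contains 0.9 for X = 6, 7, 8 or 9, total probability 65%. Most of the shortfall is X = 10, probability 0.9¹⁰ = 35%.
- True rate 70%: it contains 0.7 for X = 4 to 8, total probability 84%.

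**8. Same formula in section 8.1.2, 20/30.** Wald 49.8–83.5% (printed as 50–84%); Wilson 48.8–80.8%; Clopper-Pearson 47.2–82.7%. The lower limit there is only 1 to 3 points too high.

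**The case against.** Four points can be made in the protocol's favour.

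*The arithmetic is correct.* This stands: the printed figure is what the Wald formula gives. The fault is using that formula at this sample size and proportion.

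*No stated rule is broken.* Section 8.1.1 attaches the 70% to the percentage of patients completing. It never says that the lower confidence limit must exceed 70%, and section 8.3.2 plans descriptive analysis without a test. This stands in part. The confidence-limit reading is an inference from 71% being printed directly after 70% and from the explicit use of a lower confidence limit in section 8.1.2. It is the more natural reading, but not the only one. On the other reading the printed interval is still not a valid 95% interval.

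*The size of the error depends on the methods listed.* Also true. The likelihood-ratio limit of 62.8% is itself asymptotic, and a few methods fall outside 55.5–62.8% in either direction. Clopper-Pearson and Wilson are the two to rely on, and the conclusion about 70% is the same under every alternative tried.

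*The choice of interval belongs in the statistical analysis plan.* That holds for section 8.3.2, which does not commit the final analysis to Wald. It does not excuse a specific wrong figure printed in the protocol beside a feasibility threshold.

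The practical consequence is limited: the design is a 20-patient feasibility study, and sections 8.1.2 to 8.1.4 offer other arguments for its size.

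**Conclusion.** The interval in section 8.1.1 is wrong as written and should be corrected. For 9 of 10 completers the lower 95% limit is 55.5% (Clopper-Pearson) or 59.6% (Wilson), against 71.4% as calculated for the protocol. The overstatement is 71.4 − 55.5 = 15.9 or 71.4 − 59.6 = 11.8 points; against the likelihood-ratio limit it is still 71.4 − 62.8 = 8.6 points.

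If the 70% floor is meant for the lower confidence limit, the expected result fails it. With Clopper-Pearson no result in 10 patients passes, since even 10/10 gives 69.2%. With Wilson only 10/10 passes, which has probability 35% at a true rate of 90%. If the floor is meant for the observed proportion, the rule itself is unaffected, but the stated precision remains too favourable.

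The interval in section 8.1.2 comes from the same formula, but its error is not material. These conclusions assume a two-sided 95% interval and 10 patients in the intervention arm, as the protocol gives them.

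**What to change.** In section 8.1.1:

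1. Replace 71–100% with 55.5–99.7% (Clopper-Pearson) or 59.6–98.2% (Wilson), and name the method.
2. Use the same method when the completion proportion is reported under section 8.3.2. If Wald were carried forward, 10/10 would be reported as 100–100%.
3. State whether 70% applies to the observed proportion or to the lower confidence limit, and reword so that the text does not suggest 9 of 10 excludes a rate below 70%.
4. If 70% applies to the observed proportion, say what 10 patients can support. For example, 9 or more completers occur with probability 74% at a true rate of 90% (0.9⁹ × 1.9 = 0.736) and 15% at a true rate of 70%.

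For consistency, the interval in section 8.1.2 can be recalculated by the same method.

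The cost is the wording of one paragraph and a less favourable stated precision. The correction does not by itself call for a change in sample size, design or conduct, but section 8.1.1 should no longer be read as showing that 10 patients suffice to exclude completion below 70%.

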8.1.2 Feasibility of recruitment

Estimated cure rate with second evacuation alone is approximately 25% in our cohort³. The cure rate with single agent chemotherapy is approximately 66%. Therefore under conservative assumptions, in order to demonstrate a clinically significant benefit of pembrolizumab prior to second evacuation of 66% cure vs. second evacuation alone (25% cure), 40 patients in total are required (80% power, significance level 0.05). To justify a larger study, this cohort would be recruited in no more than 3 years (14 patients/year).

Based on current caseloads, we estimate approximately 50 patients per year in the UK are eligible for the study, of whom 30 are managed at CXH. With 30 eligible patients, assuming 66% (n=20) are recruited in 1 year, the 95% confidence interval

is 50 – 84%. This is consistent with the recruitment target of at least 15 patients per year at CXH (30 patients/year x 0.5 [lower bound of the 95% confidence interval for the recruitment rate]). Thus recruitment of 20 patients in 1 year would give us confidence that a definitive study would be feasible.

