5.4 Randomisation

After eligibility has been confirmed, patients will be randomised to the trial. Randomisation will be performed centrally by Imperial Cancer Clinical Trials Section (CCTS) using the study database. There will be no option for manual randomisation. Upon randomisation each patient will be allocated a unique subject ID which should be used in all future correspondence. Please refer to the eCRF Completion Manual for further details on patient randomisation.

RESOLVE	C/43/2022	Imperial College London	v2.0 10 th July 2023
---------	-----------	-------------------------	------------------------------------

In this open-label study, randomisation will be on a 1:1 basis between second evacuation and pembrolizumab prior to second evacuation arms. Randomisation will be stratified according to baseline hCG since this has been shown to strongly influence the probability of cure following second evacuation. Based on historical data, we have carried out simulations to show that randomising patients within pre-defined hCG values corresponding to expected median or quartile limits results in balanced distribution of hCG values between the two arms in over 95% of simulated trials. The Trial Statistician will be responsible for holding the randomisation code securely until the final analysis of the study but also to enable the interim analysis.

After eligibility has been confirmed, an archival tissue sample in the form of formalin fixed paraffin embedded (FFPE) tumour block and/or diagnostic tissue section will be collected from each patient.

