8.1.3 Detection of a clinical meaningful result

Given the challenges of carrying out definitive randomised controlled trials in the rare disease setting, data from small scale studies have been highly influential in driving treatment advances. The global adoption of pembrolizumab for GTN is a case in point. Our initial observation was exceptionally high pembrolizumab efficacy amongst a series of 4 patients. These data were sufficient to result in a change in NHS guidelines to support funding of this agent for patients with resistant disease. As we and the global community have accrued more data, use of pembrolizumab is now recommended in global GTN management guidelines.

While, as per recommendations for feasibility studies, we did not conduct sample size calculations for the pembrolizumab vs control comparison, we note that even with such a small sample size we would have adequate power to detect a clinically significant difference between the arms. Second evacuation for disease recurrence has a complete response (CR) rate of ~25% based on a study done at our centre. Amongst the remainder who relapse, we estimate a 75% CR rate to pembrolizumab based on multicentre data on patients with drug resistant, metastatic disease. We thus estimate the CR rate of neoadjuvant pembrolizumab to be 81% ($100*[0.25+(1-0.25)*0.75]$). For 80% power with α of 0.05, 9 patients per arm are required. This is consistent with 20 patients in total, randomised 1:1 to the control and neoadjuvant pembrolizumab arms.

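### The definitive-study size of 40 rests on an optimistic approximation: for 25% vs 66% cure, two-sided exact power is about 75% (chi-square) or 64% (Fisher), not 80%

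*Protocol*

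**What the plan says.** Protocol section 8.1.2 (Feasibility of recruitment) takes as its control figure: "Estimated cure rate with second evacuation alone is approximately 25% in our cohort". The target is a "benefit of pembrolizumab prior to second evacuation of 66% cure vs. second evacuation alone (25% cure"), and for this it states that "40 patients in total are required (80% power, significance level 0.05"). It names no test, sidedness or allocation ratio for that later study.

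The size then becomes a recruitment bar: "this cohort would be recruited in no more than 3 years (14 patients/year"). The section goes on to assume that 20 of 30 eligible patients at Charing Cross Hospital (CXH) are recruited in a year, and multiplies the lower 95% limit of that proportion (given as 50%) by 30. Its reading of the result is: "This is consistent with the recruitment target of at least 15 patients per year at CXH". It concludes: "Thus recruitment of 20 patients in 1 year would give us confidence that a definitive study would be feasible".

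Section 8.1.3 has a companion calculation for 25% vs 81%: "For 80% power with α of 0.05, 9 patients per arm are required". Section 5.4 gives the allocation for the present trial: "randomisation will be on a 1:1 basis between second evacuation and pembrolizumab prior to second evacuation arms".

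**The concern.** The proportion of eligible patients who consent to randomisation is a primary feasibility endpoint (section 2.1). The yardstick for recruitment is the number that a definitive trial would need, spread over 3 years. If 40 patients do not deliver the stated power at the stated level, the bar of 14 per year is set somewhat low, and a reader planning the next trial would inherit a size with less power than advertised.

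The doubt arises because 20 per arm is small for a normal approximation with unpooled variance. At that size the test implied by the formula can reject too often under the null, while tests that stay near 5% have less power than the formula suggests.

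**Working it through.** **Inputs (section 8.1.2).** p1 = 0.25, p2 = 0.66, power 80%, significance level 0.05, N = 40. Assumed: 1:1 allocation as in section 5.4 (20 per arm), and a two-sided test.

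**1. Reproducing 40.** Two-sided normal approximation with unpooled variance:

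n per arm = (z0.975 + z0.80)² × [p1(1−p1) + p2(1−p2)] / (p2−p1)²

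= (1.960 + 0.842)² × (0.1875 + 0.2244) / 0.41²

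= 7.849 × 0.4119 / 0.1681 = 19.2, so 20 per arm and 40 in total.

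For 25% vs 81% the same formula gives 8.5 (8.4 with the unrounded 81.25%), so 9 per arm, which matches section 8.1.3. One two-sided formula therefore explains both figures.

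**2. Other standard two-sided formulas for 25% vs 66%.**
- Pooled variance under the null (mean rate 0.455): [1.960 × √(2 × 0.455 × 0.545) + 0.842 × √0.4119]² / 0.1681 = 21.9, so 22 per arm and 44 in total.
- Arcsine: 44 in total.
- Pooled with continuity correction: 54 in total.

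**3. Exact performance at 20 per arm, two-sided 5%.** Every pair of outcomes (0 to 20 cures in each arm) is enumerated and weighted by its binomial probabilities. Maximum type I error is taken over common cure rates from 1% to 99%.

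| Test | Power at 25% vs 66% | Maximum type I error |
|---|---|---|
| Unpooled Wald | 82.8% | 8.1% (6.8% at a common rate of 25%) |
| Pearson chi-square | 74.5% | 5.3% |
| Fisher's exact | 63.8% | 2.5% |

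Barnard's and Boschloo's tests give 73.3%, and mid-p gives 72.8%. At the 42 patients that 14 per year would actually yield (3 × 14), chi-square power is 77.6% and Fisher 66.0%.

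**4. Size needed for 80%.**
- Chi-square: 22 per arm, 44 in total (exact power 80.2%); 44/3 = 14.7 per year.
- Fisher: first reached at 25 per arm, 50 in total (80.6%). It dips to 79.2% and 79.6% at 26 and 27 per arm, and is 81.9% at 28 per arm, 56 in total. 50/3 = 16.7 and 56/3 = 18.7 per year.
- As stated: 40/3 = 13.3, given as 14 per year.

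**5. Against the protocol's recruitment argument.** The normal-approximation lower limit for 20/30 is 49.8%, and 30 × 0.498 = 14.9 per year, rounded in the protocol to 15. Three years at 15 gives 45 patients, which covers 44 but not 50 to 56. Three years at 20 gives 60, which covers all of them.

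**The case against.** The strongest reply is that 40 is no error. A textbook formula gives it exactly, and the same formula gives the 9 per arm in section 8.1.3. That stands: a reader might infer a calculation slip, and there is none. What does not follow is that the stated pair, 80% power at 0.05, is attained. At 20 per arm, the test behind the formula exceeds 80% only with a true level well above 0.05.

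A second reply is that no test or sidedness is named, so two-sided chi-square and Fisher are a reviewer's choice; a one-sided 5% chi-square test has 83.5% power at 40. That is true, but no one-sided test is stated, and it is the two-sided formula that returns both 40 and 9. Two-sided is the natural reading, though it remains an assumption.

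A third reply concerns consequences, and most of it stands. A reader might infer that correcting the size overturns the conclusion that 20 recruits in a year show feasibility. The protocol does not support that:
- With chi-square the need rises to 14.7 per year, still within the protocol's own lower bound (14.9) and its target of 15. Failure there requires a separate change to an exact interval for 20/30 (lower limit 47.2%, or 14.2 per year).
- With Fisher, the lower-bound argument for CXH alone does fall short. However, section 8.1.2 puts UK eligibility at about 50 per year, and sections 4.1 and 8.2 provide for a second site. If the same consent rate held across the UK (an assumption), even the exact limit would give 50 × 0.472 = 23.6 per year.

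Finally, 40 is a planning figure for a hypothetical later trial. It neither sizes nor analyses this one.

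**Conclusion.** The point holds as a matter of stated power. With 1:1 allocation and a two-sided 5% level, 40 patients give about 75% power by chi-square and 64% by Fisher's exact test: shortfalls of about 5.5 and 16 percentage points. The recruitment bar of 14 per year should be about 15 with chi-square, or 17 to 19 with Fisher.

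The effect on feasibility is modest. With chi-square, the margin shrinks to one patient over 3 years (45 against 44) and the conclusion stands. With Fisher, the CXH-only lower bound of about 15 per year is not enough, though 20 per year or a second site would be. This is an optimistic approximation that should be restated, not a reversal of the feasibility case. The result takes the 25% and 66% cure rates as given.

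**What to change.** In section 8.1.2, name the test and sidedness intended for the definitive study, then do one of the following:

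- Restate the size as 44 (two-sided chi-square; 14.7, about 15 per year over 3 years) or 50 to 56 (two-sided Fisher's exact; about 17 to 19 per year), and put that rate into the recruitment criterion in place of 14 per year. If Fisher is chosen, say whether the target is to be met by CXH alone or with a second site.
- Keep 40 and state its power as about 75% (chi-square) or 64% (Fisher).

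The cost is a few restated figures. The present trial's 20 patients, endpoints and analyses do not change.
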